16.6 INSURANCE COMPENSATION

The Sponsor certifies that it has taken out a liability insurance policy covering all clinical trials under its sponsorship. This insurance policy is in accordance with local laws and requirements. The insurance of the Sponsor does not relieve the Investigator and the collaborators from any obligation to maintain their own liability insurance policy as required by applicable law. An insurance certificate will be provided to the IRBs or regulatory authorities in countries requiring this document.

16.7 SPONSOR AUDITS AND INSPECTIONS BY REGULATORY AGENCIES

For the purpose of ensuring compliance with the clinical trial protocol, GCP, and applicable regulatory requirements, the Investigator should permit auditing by or on the behalf of the Sponsor and inspection by regulatory authorities.

The Investigator agrees to allow the auditors/inspectors to have direct access to his/her study records for review, being understood that these personnel are bound by professional secrecy, and as such will not disclose any personal identity or personal medical information.

The Investigator will make every effort to help with the performance of the audits and inspections, giving access to all necessary facilities, data, and documents.

As soon as the Investigator is notified of a planned inspection by the authorities, he/she will inform the Sponsor and authorize the Sponsor to participate in this inspection.

The confidentiality of the data verified and the protection of the patients should be respected during these inspections.

Any result and information arising from the inspections by the regulatory authorities will be immediately communicated by the Investigator to the Sponsor.

The Investigator shall take appropriate measures required by the Sponsor to take corrective actions for all problems found during the audit or inspections.

16.8 PREMATURE DISCONTINUATION OF THE STUDY OR PREMATURE CLOSE-OUT OF A SITE

16.8.1 By the Sponsor

The Sponsor has the right to terminate the participation of either an individual site or the study at any time, for any reason, including but not limited to the following:

- The information on the IMP leads to doubt as to the benefit/risk ratio;
- Patient enrollment is unsatisfactory;
- The Investigator has received from the Sponsor all IMP, means and information necessary to perform the clinical trial and has not included any patient after a reasonable period of time mutually agreed upon;
- Noncompliance by the Investigator or Subinvestigator, or delegated staff with any provision of the clinical trial protocol, or breach of any applicable laws, regulations, or ICH GCP guidelines;
- The total number of patients is included earlier than expected.

In any case the Sponsor will notify the Investigator of its decision by written notice.

16.8.2 By the Investigator

The Investigator may terminate his/her participation upon 30 days' prior written notice if the study site or the Investigator for any reason becomes unable to perform or complete the clinical trial.

In the event of premature discontinuation of the study or premature close-out of a site, for any reason whatsoever, the appropriate IRB and regulatory authorities should be informed according to applicable regulatory requirements.

16.9 CLINICAL TRIAL RESULTS

The Sponsor will be responsible for preparing a clinical study report and to provide a summary of study results to Investigator.

When the data from all investigational sites have been fully analyzed by the Sponsor, the latter will communicate the results of the clinical trial to the Investigator(s).

16.10 PUBLICATIONS AND COMMUNICATIONS

The Investigator undertakes not to make any publication or release pertaining to the study and/or results of the study prior to the Sponsor's written consent, being understood that the Sponsor will not unreasonably withhold his approval.

As the study is being conducted at multiple sites, the Sponsor agrees that, consistent with scientific standards, a primary presentation or publication of the study results based on global study outcomes shall be sought. However, if no multicenter publication is submitted, underway, or planned within 12 months of the completion of this study at all sites, the Investigator shall have the right to publish or present independently the results of this study. The Investigator shall provide the Sponsor with a copy of any such presentation or publication for review and comment at least 30 days in advance of any presentation or submission for publication. In addition, if requested by the Sponsor, any presentation or submission for publication shall be delayed for a limited time, not to exceed 90 days, to allow for filing of a patent application or such other justified measures as the Sponsor deems appropriate to establish and preserve its proprietary rights.

The Investigator shall not use the name(s) of the Sponsor and/or of its employees in advertising or promotional material or publication without the prior written consent of the Sponsor. The Sponsor shall not use the name(s) of the Investigator and/or the Collaborators in advertising or promotional material or publication without having received his/her and/or their prior written consent(s).

The Sponsor has the right at any time to publish the results of the study.

17 CLINICAL TRIAL PROTOCOL AMENDMENTS

All appendices attached hereto and referred to herein are made part of this clinical trial protocol.

The Investigator should not implement any deviation from, or changes of the clinical trial protocol without agreement by the Sponsor and prior review and documented approval/favorable opinion from the IRB of an amendment, except where necessary to eliminate an immediate hazard(s) to clinical trial patients, or when the change(s) involves only logistical or administrative aspects of the trial. Any change agreed upon will be recorded in writing, the written amendment will be signed by the Investigator and by the Sponsor and the signed amendment will be filed with this clinical trial protocol.

Any amendment to the clinical trial protocol requires written approval/favorable opinion by the IRB prior to its implementation, unless there are overriding safety reasons.

In some instances, an amendment may require a change to the informed consent form. The Investigator must receive an IRB approval/favorable opinion concerning the revised informed consent form prior to implementation of the change and patient signature should be recollected if necessary.

19 APPENDICES

Appendix A ECOG Performance Status Scale

Performance Status	Description
0	Normal, fully functional
1	Fatigue without significant decrease in daily activity
2	Fatigue with significant impairment of daily activities or bedrest <50% of waking hours
3	Bedrest/sitting>50% of waking hours
4	Bedridden or unable to care for self

Appendix B National Cancer Institute Common Terminology Criteria for Adverse Events

Refer to NCI CTC AE v.4.03 ([15](#)) in the Study Reference Manual, or online at the following NCI website: <http://ctep.cancer.gov/reporting/ctc.html>

- Toxicity grade should reflect the most severe degree occurring during the evaluated period, not an average.
- When 2 criteria are available for similar toxicities, the one resulting in the more severe grade should be used.
- The evaluator must attempt to discriminate between disease/treatment and related signs/symptoms.
- An accurate baseline prior to therapy is essential.

Appendix C IMWG Response Criteria

Disease response will be assessed using the updated International Myeloma Working Group Response Criteria (IMWG)(10).

A confirmation assessment within 4 weeks (± 3 days) for disease response evaluation assessments is required in this protocol, including MR.

Table 9 - International Myeloma Working Group Response Criteria

Response	IMWG criteria
sCR	CR as defined below plus: 
Normal FLC ratio andAbsence of clonal cells in bone marrow by immunohistochemistry or 2 – 4 color flow cytometry
CR	
Negative immunofixation on the serum and urine andDisappearance of any soft tissue plasmacytomas and<5% plasma cells in bone marrow.In patients with only FLC disease, a normal FLC ratio of 0.26–1.65 is required.
VGPR	
Serum and urine M-protein detectable by immunofixation but not on electrophoresis or$\geq 90\%$ reduction in serum M-protein plus urine M-protein level <100 mg/24 h.In patients with only FLC disease, $>90\%$ decrease in the difference between involved and uninvolved FLC levels is required.
PR	
$\geq 50\%$ reduction of serum M-protein and reduction in 24 hours urinary M protein by $\geq 90\%$ or to <200 mg/24 hIf the serum and urine M-protein are unmeasurable, a $\geq 50\%$ decrease in the difference between involved and uninvolved FLC levels is required in place of the M-protein criteriaIf serum and urine M-protein are not measurable, and serum free light assay is also not measurable, $\geq 50\%$ reduction in plasma cells is required in place of M-protein, provided baseline bone marrow plasma cell percentage was $\geq 30\%$In addition to the above listed criteria, if present at baseline, a $\geq 50\%$ reduction in the size of soft tissue plasmacytomas is also required
SD	
Not meeting criteria for CR, VGPR, PR or progressive disease
PD	Increase of $\geq 25\%$ from lowest response value in any one of the following: 
Serum M-component (the absolute increase must be ≥ 0.5 g/dL) and/orUrine M-component (the absolute increase must be ≥ 200 mg/24 h) and/orOnly in patients without measurable serum and urine M-protein, the difference between involved and uninvolved FLC levels. The absolute increase must be >10 mg/dLOnly in patients without measurable serum and urine M-protein and without measurable disease by FLC levels, bone marrow plasma cell percentage (absolute % must be $\geq 10\%$)Definite development of new bone lesions or soft tissue plasmacytomas or definite increase in the size of existing bone lesions or soft tissue plasmacytomasDevelopment of hypercalcemia (corrected serum calcium >11.5 mg/dL) that can be attributed solely to the plasma cell proliferative disorder

All response categories (CR, sCR, VGPR, PR and PD) require two consecutive assessments made at any time before the institution of any new therapy; complete response and PR and SD categories also require no known evidence of progressive or new bone lesions if radiographic studies were performed. VGPR and CR categories require serum and urine studies regardless of whether disease at baseline was measurable in serum, urine both or either. Radiographic studies

are not required to satisfy these response requirements. Bone marrow assessments need not be confirmed. For progressive disease, serum M-component increases of ≥ 1 g/dL are sufficient to define response if starting M-component is ≥ 5 g/dL.

IMWG clarification for coding PD: Clarified that Bone marrow criteria for PD are to be used only in patients without measurable disease by M protein and by FLC levels. Clarified that 25% increase refers to M protein, FLC, and bone marrow results and does not refer to bone lesions, soft tissue plasmacytomas or hypercalcemia. Note the lowest response value does not need to be a confirmed value.

Table 10 - Additional response criteria for specific disease states

Minor/ minimal response(MR) in patients with relapsed and refractory myeloma adapted from the EMBT criteria	$\geq 25\%$ but $\leq 49\%$ reduction of serum M protein and reduction in 24 hour urine M protein by 50 – 89%, which still exceeds 200 mg/24 hrs. In addition to above; if present at baseline, 25-49% reduction in the size of soft tissue plasmacytomas is also required. No increase in size or number of lytic bone lesions (development of compression fractures does not exclude response).
Immunophenotypic CR	Stringent CR plus Absence of phenotypic aberrant PC (clonal) in bone marrow with a minimum of one million of total BM cells analyzed by multiparametric flow cytometry (with ≥ 4 colors)
Molecular CR	Stringent CR plus negative ASO-PCR (sensitivity 10^{-5})

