	
Dose escalation will be stopped if $\geq 33\%$ (≥ 2 in up to 6 patients) of patients experienced an IMP related DLT observed during the first cycles of treatment (4 weeks), according to the definition of MAD.
 
Phase II part
 
ORR is defined as the proportion of patients with stringent complete response (sCR), complete response (CR), very good partial response (VGPR), and partial response (PR) based on responses as assessed by the Independent Adjudication Committee (IAC) using the International Myeloma Working Group (IMWG) Uniform Response Criteria.
 
Response evaluation will include:
 
• M-protein quantification (serum and 24-hr urine)• Serum free light chain levels• Bone marrow aspiration and/ or biopsy• CT/MRI scan of plasmacytoma• Bone skeletal survey• Corrected serum calcium 
Secondary endpoint:
 
Safety profile of isatuximab in terms of treatment-emergent adverse events/ serious adverse events (TEAE/SAE) and changes in laboratory parameters, vital signs, ECGs and assessment of physical examination.
 
Assessment of efficacy:
 
Efficacy will be determined using IMWG defined response criteria. Efficacy parameters will include Overall Response Rate (ORR), Clinical Benefit Rate (CBR), Overall Survival (OS), Progression Free Survival (PFS), Duration Of Response (DOR) and Time To Progression (TTP).
 
PK assessments:
 
• Concentration observed at the end of an intravenous (IV) infusion (C_{eoI})• Maximum observed concentration (C_{max})• Time to reach the maximum concentration (T_{max})• Concentrations just before drug infusion (C_{trough})• AUC over the dosing interval ($AUC_{1\text{week}}$) 
CD38 receptor density assessment:
 
• CD38 receptor density from baseline bone marrow aspirates. 
Immune response:
 
• Level of Anti -drug antibodies (ADA). 
Results of additional procedures performed as part of standard of care to assess the current disease status may also be collected.
 
Exploratory Endpoints:
 
• MRD by sequencing will be assessed in patients achieving a CR.• Bone marrow samples will be analyzed for multiple myeloma molecular subtype (by cytogenetics/ FISH).• Blood samples will be analyzed for immune genetic determinants (including FcγR polymorphisms, HLA and KIR genotypes).
--	---

[figure not shown]

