15. Serum chemistry includes: SGOT (AST), SGPT (ALT), bilirubin (total and direct), alkaline phosphatase, lactate dehydrogenase (LDH), fasting glucose, sodium, potassium, magnesium, chloride, calcium, corrected serum calcium, phosphate, uric acid, blood urea nitrogen (BUN), serum creatinine and eGFR (Revised equations for eGFR in Japanese), albumin and total protein. To be done at screening, then prior to pre-medication and IMP administration on Day 1, Day 8, Day 15 and Day 22 of Cycle 1 and on Day 1 and Day 15 of every subsequent cycle, at the EoT visit and as clinically indicated.
16. Coagulation: To be done at screening and then as clinically indicated. Coagulation includes: Prothrombin time (PT) or international normalized ratio (INR) and activated partial thromboplastin time (aPTT).
17. Urinalysis includes: blood, protein, glucose, pH, ketones, bilirubin, leucocytes, nitrites and specific gravity. To be done at baseline, on Day 1 and Day 15 of each cycle, EoT, and if clinically indicated. Quantitative urinalysis will be needed if hematuria is observed or clinically indicated.
18. Pregnancy Test: Women of child bearing potential must have a negative serum pregnancy test result within 7 days prior to first IMP administration and at the EoT visit. Urine test can be used at Day 1 of each subsequent cycle.
19. HBc-Ab, HBs-Ab test: If HBc-Ab and/or HBs-Ab positive at baseline, Hepatitis B Virus (HBV)-DNA test is required prior to registration. If history of HBV infection is suspected, monitoring of HBV-DNA is recommended on Day 1 of each cycle, EoT and if clinically indicated.
20. Once at any time if HBV status unknown before treatment started and to be repeated if clinically indicated.
21. Myeloma-specific Lab Tests: serum electrophoresis, immunoglobulin assay, corrected serum calcium and 24-hour urine collection for Bence Jones protein to be performed at baseline prior to administration, prior to each cycle thereafter and at time of study discontinuation (if last tests were >4 weeks). Serum β 2 microglobulin to be performed at baseline prior to administration, EoT and if clinically indicated. Immunofixation and free light chain tests to be performed at baseline prior to administration, EOT, if CR is suspected and if clinically indicated.

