4 INTRODUCTION AND RATIONALE

4.1 INTRODUCTION

CD38 is a type II glycosylated 45 kilodalton (kDa) membrane protein that was identified as a lymphocyte marker (1). CD38 has a role in leukocyte homeostasis through modulation of hematopoietic cell survival and differentiation. CD38 functions as a receptor binding to CD31 and is involved in cell adhesion and signal transduction. The function of CD38 in signal transduction appears to be versatile depending on the cell lineage, the differentiation stage, and, possibly, the association with different co-receptors (2). CD38 is also an ecto-enzyme catalyzing the synthesis and hydrolysis of cyclic adenosine-diphosphate-ribose (cADPR) from nicotinamide adenine dinucleotide (NAD⁺) to ADP-ribose (3). These reaction products are implicated in calcium mobilization and intracellular signaling.

The expression of CD38 in healthy humans can be detected on NK cells, monocytes, dendritic cells, macrophages, granulocytes, activated T and B cells, and plasma cells. In contrast, expression has not been detected in hematopoietic stem cells, resting T and B cells, or tissue macrophages. Several hematological malignancies express CD38 including those of B-lymphocyte, T-lymphocyte and myeloid origin. Moreover, CD38 was identified as a negative prognostic marker in some hematological malignancies, such as CLL. The expression of CD38 is especially notable in multiple myeloma (MM) as >98% of patients are positive for this protein (4, 5). The strong and uniform expression of CD38 on malignant clonal MM cells contrasts with the restricted expression pattern on normal cells suggesting this antigen may be useful for specific targeting of tumor cells.

Isatuximab (SAR650984) is a naked IgG1 kappa monoclonal antibody (mAb) directed against CD38, a receptor antigen expressed on hematopoietic cells. Isatuximab is produced in a mammalian cell line (Chinese Hamster Ovary) using recombinant DNA technology. The monoclonal anti-body isatuximab has 4 modes of action to kill target cells:

- Anti-body-dependent cell mediated cytotoxicity (ADCC)
- Complement-dependent cytotoxicity (CDC)
- Pro-apoptotic activity
- Inhibition of CD38 enzyme activity (6)

In preclinical tumor models in mice, it was active as a single agent and in combination with reference treatments, on several CD38-positive tumors in multiple hematological malignancies, including multiple myeloma (MM), non-Hodgkin's-lymphoma and leukemia.

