6.2.1 Dose Levels

- Phase I part Cohort 1: 1/2 of global maximum administrated dose defined in TED10893 (ie. 10 mg/kg QW in Cycle 1 (4 weeks) followed by 10 mg/kg Q2W in subsequent cycles)
- Phase I part Cohort 2: Global recommended dose defined in TED10893 (ie. 20 mg/kg QW in Cycle 1 (4 weeks) followed by 20 mg/kg Q2W in subsequent cycles)
- Phase II part: Recommended dose level defined in Phase I part (10 mg/kg or 20 mg/kg QW in Cycle 1 (4 weeks) followed by Q2W in subsequent cycles)

No additional or intermediate dose level is planned in this study. Refer to [Section 1.2](#) for the treatment schema.

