7.2 INCLUSION CRITERIA

- I 01. Males or females, age 20 years or older.
- I 02. Patient must have a known diagnosis of symptomatic multiple myeloma.
- I 03. Patients must have received at least 3 prior lines of therapies which must include treatment with an Immunomodulatory Drug (IMiD, eg. Lenalidomide, Pomalidomide or Thalidomide) AND a Proteasome Inhibitor (PI, eg. Bortezomib). The patients must have received an IMiD and a PI for ≥ 2 cycles or ≥ 2 months of treatment.
OR
Patients whose disease is double refractory to an IMiD and a PI. For patients who have received more than one type of IMiD and PI, their disease must be refractory to the most recent one. The patients must have received an IMiD and a PI for ≥ 2 cycles or ≥ 2 months of treatment.
- I 04. Subject must have been responsive (ie. Minimal Response [MR] or better) to at least one prior line of therapy.
- I 05. Refractory to the most recently received IMiD or PI included therapy (patient must progress during or within 60 days of completion of treatment with IMiD or PI).
- I 06. Patients with measurable disease defined as at least one of the followings:
 - IgG Type: Serum M-protein ≥ 1 g/dL (≥ 10 g/L)
 - IgA Type: Serum M-protein ≥ 0.5 g/dL (≥ 5 g/L)
 - IgD Type: Serum M-protein ≥ 0.5 g/dL (≥ 5 g/L)
 - Urine M-protein ≥ 200 mg/24 hours
- I 07. Patients with a Eastern Cooperative Oncology Group (ECOG) performance status ≤ 2
- I 08. Life expectancy of at least 3 months.
- I 09. Female patients of childbearing potential (FCBP) and male patients with female partners of childbearing potential who agreed to avoid pregnancy by using an adequate method of contraception for 2 weeks prior to screening, during and 6 months after the last administration of the IMP. Acceptable and effective methods of contraception includes 2 barrier method or 1 barrier method with a spermicide (spermicide is only available for purchase with condoms or diaphragm), oral hormonal contraception, intra-uterine

hormone-releasing system, vasectomy or intrauterine device. Adequate methods of contraception are provided as examples. Other acceptable and effective methods of birth control are also permitted.

A FCBP is a sexually mature woman who: 1) has not undergone a hysterectomy or bilateral oophorectomy; or 2) has not been naturally postmenopausal for at least 24 consecutive months.

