Appendix I CD38 blood test interference guideline AABB2016

Advancing Transfusion and
Cellular Therapies Worldwide

Association Bulletin #16-02

Date: January 15, 2016
To: AABB Members
From: ██████████—President
██████████—Chief Executive Officer
Re: Mitigating the Anti-CD38 Interference with Serologic Testing

Summary

A new class of therapeutic agents for multiple myeloma, CD38 monoclonal antibodies, can result in interference with blood bank serologic tests and thereby cause delays in issuing Red Blood Cell (RBC) units to patients receiving these agents. To minimize these delays, hospitals should set up procedures to inform the transfusion service when patients start receiving these agents. Considerations for the transfusion service, both before and after initiation of anti-CD38 therapy, are detailed below.

The AABB Clinical Transfusion Medicine Committee has developed this bulletin to provide background information and guidance to members regarding anti-CD38 interference with serologic testing. The bulletin includes recommendations for its prevention and treatment.

Association Bulletins, which are approved for distribution by the AABB Board of Directors, may include announcements of standards or requirements for accreditation, recommendations on emerging trends or best practices, and/or pertinent information. This bulletin contains information and recommendations. No new standards are proposed.

Background

CD38 monoclonal antibodies are a new treatment for multiple myeloma

CD38, an integral membrane protein that is highly expressed on myeloma cells, has been identified as an effective target antigen for monoclonal antibody therapies. In November 2015, the first therapeutic CD38 monoclonal antibody [daratumumab (Darzalex, Janssen Biotech, Horsham, PA)] was approved by the Food and Drug Administration.¹ Other CD38 monoclonal antibodies are under development.

CD38 monoclonal antibodies interfere with blood bank serologic tests

CD38 is weakly expressed on red cells. Anti-CD38 binds to CD38 on reagent RBCs, causing panreactivity in vitro.^{2,3} Plasma samples from anti-CD38-treated patients consistently cause positive reactions in indirect antiglobulin tests (IATs), antibody detection (screening) tests, antibody identification panels, and antihuman globulin (AHG) crossmatches. Agglutination due to anti-CD38 may occur in all media (eg, saline, low ionic strength saline, polyethylene glycol),

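### CR requires negative serum immunofixation with no rule for the drug's own IgG-kappa band, so an IgG-kappa patient otherwise in CR may be recorded as VGPR

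*Protocol*

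**What the plan says.** Protocol Appendix C, Table 9 requires "Negative immunofixation on the serum and urine" for CR, together with resolved plasmacytomas and fewer than 5% marrow plasma cells. sCR builds on CR. One route into VGPR is "Serum and urine M-protein detectable by immunofixation but not on electrophoresis". The table makes no exception for a band that comes from the drug.

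Protocol Section 4.1 describes the product: "Isatuximab (SAR650984) is a naked IgG1 kappa monoclonal antibody (mAb) directed against CD38". Section 6.2.1 gives the higher dose level as "20 mg/kg QW in Cycle 1 (4 weeks) followed by 20 mg/kg Q2W in subsequent cycles", and Section 8.1.2 continues dosing until progression or another stopping reason. Inclusion criterion I 06 (Section 7.2) admits IgG disease by M-protein level ("IgG Type: Serum M-protein" of at least 1 g/dL) with no light-chain restriction, so IgG-kappa patients are eligible.

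On timing, footnote 21 in Section 1.6 says: "Immunofixation and free light chain tests to be performed at baseline prior to administration, EOT, if CR is suspected and if clinically indicated". Footnote 1 makes assessments pre-dose by default.

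On MRD, the synopsis states "MRD by sequencing will be assessed in patients achieving a CR", and Section 9.4.2 likewise refers to CR patients. The marrow sample, however, is taken when CR is suspected (footnotes 27 and 28; Section 12.3.1).

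The protocol does recognise interference by this drug class, but only for red-cell testing: Appendix I carries the statement "CD38 monoclonal antibodies interfere with blood bank serologic tests", and the patient-card, blood-bank and Coombs items in footnotes 6 and 13 serve the same purpose.

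**The concern.** Immunofixation identifies a monoclonal band by heavy-chain and light-chain type. When the patient's own protein is IgG kappa, a residual disease band and a drug band have the same type, so the test that separates CR from VGPR may not separate disease from treatment. The sponsor carried the interference problem to the blood bank but not to the response criteria.

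The stake is depth of response. BOR category is reported, broken down by subgroup (Phase 2 SAP Section 2.1.3.1, Table 4) and tabulated against CD38 receptor density and genotype (Sections 2.4.8.1 and 2.4.8.2). Any misclassification runs one way, from CR or sCR to VGPR, and it also removes patients from the CR-defined MRD endpoint. With few deep responders expected, one or two moves could visibly change the reported CR rate.

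**Working it through.** The plan states no figure on this point, so there is none to reproduce. The check has four parts.

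**1. Is there a rule anywhere?** The response text in Protocol Section 9.3.1 and Appendix C, and the Phase 2 SAP (Sections 2.1.3, 2.4.4 and 2.4.8), contain no instruction on identifying or classifying a drug band. Protocol Section 6.9.2 refers to an IAC charter, which is not among the documents.

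**2. Could the band be visible?** The documents give no distribution volume, half-life or immunofixation detection limit. Assumptions: V = 0.04 to 0.10 L/kg, half-life h = 7 to 28 days, detection limit about 0.05 to 0.5 g/L. Superposing the protocol schedule in one compartment:

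C(t) = Σ (dose/V) × 2^(−(t − tᵢ)/h), over doses given before day t.

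At 20 mg/kg, dose/V runs from 20/0.10 = 200 mg/L (0.20 g/L) to 20/0.04 = 500 mg/L (0.50 g/L).

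| Time point | Low end (V 0.10, h 7) | High end (V 0.04, h 28) |
|---|---|---|
| Pre-dose Cycle 2 Day 1 (day 28) | 0.20 × (1/16 + 1/8 + 1/4 + 1/2) = 0.20 × 0.9375 = 0.19 g/L | 0.50 × (0.500 + 0.595 + 0.707 + 0.841) = 0.50 × 2.643 = 1.32 g/L |
| Pre-dose Cycle 4 Day 1 (day 84, eight earlier doses) | 0.20 × 0.336 = 0.07 g/L | 0.50 × 2.471 = 1.24 g/L |
| 30 days after a last dose on Cycle 3 Day 15 | 0.01 g/L | 0.83 g/L |

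At 10 mg/kg each value is half. The assumed detection limit overlaps the on-treatment range, so a visible band is plausible but not established.

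**3. How many patients are exposed?** Design ORR 28% and 33 to 36 patients (Protocol Section 13.1); IgG-kappa share assumed 25 to 40%.

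- Expected responders: 33 × 0.28 = 9.2 to 36 × 0.28 = 10.1.
- IgG-kappa responders: 9.2 × 0.25 = 2.3 to 10.1 × 0.40 = 4.0.

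So about 2 to 4 responders of any depth are exposed. Only those who meet every other CR criterion can be misclassified, and the documents give no expected CR rate from which to count them.

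**4. Does it reach the primary result?** ORR counts sCR, CR, VGPR and PR, and CBR adds MR (Phase 2 SAP Sections 2.1.3.1 and 2.1.3.2). With the plan's 8 responders of 33, moving 0, 1, 2 or 3 patients from CR to VGPR leaves ORR at 8/33 = 24.2% each time. For an IgG patient entering at 1 g/dL (10 g/L), the PR cut is 5 g/L, well above the 1.32 g/L maximum from drug alone.

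**The case against.** **The mechanism rests on outside figures.** True: band visibility is assumed, not documented. Protocol Section 4.4.3 also reports nonlinear clearance and high variability, with low exposure in some patients at 10 mg/kg every 2 weeks, which simple superposition ignores. This limits the claim to a possibility in some patients. It does not close the gap in the rule.

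**The band may clear.** Responders who stop for reasons other than progression are assessed every 4 weeks, with immunofixation to confirm CR (Protocol footnote 23, Sections 12.5 and 12.6). Appendix C accepts consecutive assessments at any time before new therapy. Some patients could therefore be reclassified off drug. This does not help a patient who stays on treatment, and the assumed 30-day range still overlaps the detection limit.

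**The IAC may handle it.** The committee consists of myeloma experts working to a charter, and baseline immunofixation is available as a comparator (Section 12.2). If the charter holds a rule, a cross-reference in the SAP is still needed.

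**MRD is not lost.** A reader might infer that an affected patient can never trigger MRD testing. The text does not support that: suspected CR is the trigger, and immunofixation is itself ordered at that point. The Phase 2 SAP listings of MRD-negative patients (Section 2.4.4.2) and of response data for patients with MRD (Section 2.4.8.3) are not restricted to CR. What stands is that the patient falls outside the MRD endpoint as defined.

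**Low stakes.** CR rate is not a tested endpoint, MRD is exploratory, and any error is conservative for the drug. That sets the weight of the point, but a known one-directional error in reported depth of response is still worth removing when the data are already collected.

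**Conclusion.** The point holds in a limited form. Applied literally, Table 9 can place an IgG-kappa patient who is otherwise in CR into VGPR because of a drug band, and no rule in the protocol or SAP prevents this. The possible effect is confined to the CR/sCR versus VGPR split and to membership of the CR-defined MRD set.

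Two stronger readings should be resisted. One is that the primary analysis is biased; it is not, because both categories count as response. The other is that all IgG-kappa patients are affected. The assumed share gives about 8 to 14 of the 33 to 36 patients (33 × 0.25 = 8.3; 36 × 0.40 = 14.4), but that counts everyone with the subtype. The exposed group is about 2 to 4 responders, and the misclassified number is smaller by an unknown amount.

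The conclusion depends on the assumed drug levels, detection limit and IgG-kappa share, and on the unseen IAC charter not already containing a rule.

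**What to change.** Keep the main BOR table on Table 9. Add one rule to the Phase 2 SAP, cross-referring to the IAC charter. Flag as 'VGPR, drug interference not excluded' any patient with IgG-kappa disease at baseline whose only failed CR criterion is a residual IgG-kappa band on serum immunofixation. That means all of the following:

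- no M-protein on serum and urine electrophoresis;
- negative urine immunofixation;
- fewer than 5% marrow plasma cells;
- plasmacytomas resolved, if present at baseline;
- two consecutive assessments, as Appendix C requires.

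Report the CR-or-better rate with and without flagged patients. List them with any MRD result and any off-treatment immunofixation.

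The cost is one SAP rule, one table row and a short listing, using assessments already in the protocol. The downside is that the sensitivity CR rate may include some patients with true residual disease. The flag will also miss a patient with no marrow sample, or one whose drug level is high enough to show on electrophoresis, so it may not capture every exposed patient.
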